### 3.7.2.1 Analyses of Percent Change

Percent change in hepatic fat fraction =  $100 \times (\text{Week 12} - \text{Baseline}) / \text{Baseline}$ .

An analysis will be performed on the percent change from baseline to Week 12 in hepatic fat fraction by MRI-PDFF. An analysis of covariance (ANCOVA) model with treatment as a factor will be analyzed. The SAS sample code is listed:

```
*****

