9.14 Proton Density Fat Fraction Magnetic Resonance Imaging

Patients will undergo MRI-PDFF at the Screening Visit (Week -6 to 0), Main Study Weeks 12 and 36, and the Early Termination Visit, and Extension Study Weeks 12 and 36 and the Extension Study Early Termination Visit. The Screening Visit MRI-PDFF will be used as baseline and should be obtained as close to randomization as possible. The MRI-PDFFs will be read by a central reader.

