10.2 Statistical Methods

10.2.1 Analysis of Efficacy

10.2.1.1 Primary efficacy analysis

The primary efficacy variable will be the percent change in MRI-PDFF from baseline to Week 12. Summary statistics (number of patients, mean, standard deviation, median, minimum, and maximum) at all visits and change from baseline will be provided. The primary efficacy analysis will be analyzed with an analysis of covariance (ANCOVA) model with treatment as a factor. For any patients in the ITT Population with a missing primary efficacy parameter, the control (placebo)-based pattern mixture model will be used. Based on PK obtained in healthy volunteers dosed for up to two weeks on doses of MGL-3196 from 20-200 mg per day, a significant fraction of patients randomized to an 80 mg dose may have their dose reduced to 60 mg after PK assessment at Week 2. The multiplicity (MGL-3196 60 mg versus placebo and MGL-3196 80 mg versus placebo) will be controlled by Dunnett's Test. The primary efficacy analysis will be performed based on the ITT Population and repeated based on the Per Protocol Population.

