** PCPDFF = Percent change in MRI-PDFF from Baseline to Week 12  **
** Trt = Treatment group                                         **
*****
PROC GLM data=EFF;
  CLASS Trt;
  MODEL PCPDFF = Trt;
  LSMEANS Trt / e diff cl;
RUN;
```

In this analysis, the treatment group will be either MGL-3196 active or placebo. A pairwise comparison will be performed between MGL-3196 active and placebo. LS means for the treatment difference, 95% confidence interval and p-value will be provided.

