### 3.7.2.2 Analyses of Absolute Change

Absolute change in hepatic fat fraction = Week 12 – Baseline.

An analysis will be performed on the absolute change from baseline to Week 12 in hepatic fat fraction by MRI-PDFF. An analysis of covariance (ANCOVA) model with treatment as a factor and baseline value as a covariate will be analyzed. The SAS sample code is listed:

```
*****

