### 3.7.2.3 Week 12 Hepatic Fat Fraction Treatment Goals

There are three treatment goal endpoints that will be used to evaluate the treatment effect.

- % Change from baseline to Week 12 < -30% (% reduction of 30% or more),

- Change from baseline to Week 12  $< -5\%$  (absolute reduction of 5% or more), and
- Week 12 hepatic fat fraction  $< 5\%$ .

For each endpoint, a logistic regression model with treatment as a factor and baseline as a covariate will be used to compare the percentages of patients meeting the following treatment goals between the MGL-3196 versus placebo. The odds ratio, confidence interval, and p-value from the logistic regression will be provided.

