#### 3.7.4.1 Liver Enzyme (ALT, AST, and GGT)

The same ANCOVA model for the percent change and change in hepatic fat fraction will be used for analyzing the percent change and change from baseline to Week 12 in ALT, AST, and GGT. That is, the percent change and change from baseline to Week 12 in ALT or AST will be analyzed with the ANCOVA model with treatment as a factor. Baseline ALT, AST, or GGT value will be a covariate in the change from baseline analysis. A pairwise comparison will be

performed between MGL-3196 active and placebo. LS means for the treatment difference, 95% confidence interval and p-value will be provided.

These analyses will be repeated at the Week 30, Week 36 and Week 38 time points for the mITT population. From the results of Week 36 and 38, the sustainability of drug effect will be evaluated.

Moreover, the analyses will also be repeated for the following derived values:

- The lowest ALT, AST, or GGT endpoint value from Week 30 and Week 36. If a patient terminated early, the lowest value from the early termination visit and the previously scheduled visit will be considered the lowest value; and
- The lowest ALT, AST, or GGT value after Week 12 and through Week 36.

Unscheduled visits will not be included in these derivations.

Analyses of ALT will be repeated for females with baseline ALT  $\geq 30$  U/L and males with baseline ALT  $\geq 45$  U/L.

The Mixed Model for Repeated Measurements (MMRM) will be used to test the robustness of the results of treatment comparison at each visit. The treatment difference will be estimated from the model for Weeks 12, 30 and 36.

Analyses of ALT, AST, and GTT may be performed for the following subgroups:

- Week 12 SHBG group ( $\geq 75\%$ ,  $< 75\%$  change from baseline to Week 12) for men and women separately;
- Week 36 SHBG group ( $\geq 88\%$ ,  $< 88\%$  change from baseline to mean SHBG post Week 12 through Week 36);
- Exposure group (AUC  $< 2700$  ng\*hr/mL, AUC  $\geq 2700$  ng\*hr/mL);
- Females with baseline ALT  $\geq 30$  U/L and males with baseline ALT  $\geq 45$  U/L; and
- Any other data driven groups.

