### 3.7.4.2 Lipid Measurements

All lipid measurements will be summarized by visit, as well as absolute and percent change from baseline to each post-baseline visit.

The same ANCOVA model as primary efficacy analysis will be used for analyzing the percent change and change:

- From baseline to Week 4,
- From baseline to Week 12 with LOCF (after Day 1 and up to Week 12),
- From baseline to Week 30 with LOCF (after Week 12 and up to Week 30),
- From baseline to Week 36 with LOCF (after Week 12 and up to Week 36),
- Average between Week 30 and Week 36, and
- Average between Week 16 and Week 36

for direct LDL-C, triglycerides, Lp(a), HDL, Non-HDL, Total Cholesterol, Apo C-III (after Week 12 only), and Apo B.

Lp(a) will be analyzed separately for baseline value  $\leq 10$  nmol/L and baseline value  $> 10$  nmol/L. In the ANCOVA model for change from baseline, baseline value will be included as a covariate. But the covariate of baseline value will not be included in the model for the analysis of percent change from baseline.

If skewness from normality is observed for triglycerides data, then the triglycerides value will be logarithm-transformed before fitting the ANCOVA model. The treatment difference between two visits will then be transformed back as the percent change from. If the normality assumption still can't be satisfied with the logarithm-transformed data, a non-parametric approach (Wilcoxon rank-sum test) will be used to compare the difference in median TG change or percent change between treatment groups.

A logistic regression model with treatment as a factor and baseline as a covariate may be used to compare the percentages of patients who achieve a change from baseline to endpoint in Lp(a) ( $\leq 10$  nmol/L vs.  $> 10$  nmol/L) between the MGL-3196 dose versus placebo. The odds ratio, confidence interval, and p-value will be provided.

Analyses of lipids may be performed for the following subgroups:

- Week 12 SHBG group ( $\geq 75\%$ ,  $< 75\%$  change from baseline to Week 12) for men and women separately;
- Week 36 SHBG group ( $\geq 88\%$ ,  $< 88\%$  change from baseline to mean SHBG post Week 12 through Week 36);
- Exposure group (AUC  $< 2700$  ng\*hr/mL, AUC  $\geq 2700$  ng\*hr/mL);
- Baseline Direct LDL Category ( $< 100$  mg/dL,  $\geq 100$  mg/dL);
- Baseline Triglycerides Category ( $\leq 150$  mg/dL,  $> 150$  mg/dL); and
- Any other data driven groups.

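### The primary Week 12 percent-change model is labelled ANCOVA but contains treatment only; baseline fat fraction is in hand for every evaluable patient, and adding it could improve precision if it predicts percent change.

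*SAP*

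**What the plan says.** Protocol 10.2.1.1 states: "The primary efficacy analysis will be analyzed with an analysis of covariance (ANCOVA) model with treatment as a factor". It names no covariate, and the Synopsis reads the same way. SAP 3.7.2.1 repeats this ("An analysis of covariance (ANCOVA) model with treatment as a factor will be analyzed"), and its sample code has one right-hand term: "MODEL PCPDFF = Trt".

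The neighbouring analyses of the same scans do use baseline:

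- Absolute change, SAP 3.7.2.2: "An analysis of covariance (ANCOVA) model with treatment as a factor and baseline value as a covariate will be analyzed".
- Responder goals, SAP 3.7.2.3: "a logistic regression model with treatment as a factor and baseline as a covariate will be used". One of these goals is the 30% cut of the same percent change.

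Other percent-change endpoints leave it out:

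- Liver enzymes, SAP 3.7.4.1: "Baseline ALT, AST, or GGT value will be a covariate in the change from baseline analysis". Only the change analysis is given the covariate.
- Lipids, SAP 3.7.4.2: "But the covariate of baseline value will not be included in the model for the analysis of percent change from baseline".
- Week 36 MRI-PDFF, SAP 3.7.2.5, follows the Week 12 analysis.

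The baseline scan exists by design. Protocol 9.14: "The Screening Visit MRI-PDFF will be used as baseline and should be obtained as close to randomization as possible". The MRI-PDFF Evaluable Population (SAP 3.2.3) requires valid scans at both baseline and Week 12.

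**The concern.** A model with treatment as its only term is not an analysis of covariance, so label and code disagree. The choice also sits oddly with the rest of the section: the 30% responder cut is adjusted for baseline, while the continuous variable it is cut from is not. No reason is given.

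Dividing by baseline is not the same as adjusting for it. Any noise in the screening scan enters the denominator, so a value that is high by chance tends to produce a larger percent fall. That same scan must reach a 10% fat threshold for entry (inclusion criterion 5, with a limited exception down to 9%), which makes some regression to the mean plausible. Protocol 5.3 describes 2:1 randomization without stratification on baseline fat, and no baseline-adjusted sensitivity analysis of the Week 12 percent change is specified.

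At stake are the width of the primary interval and whether a reader can tell if a chance baseline difference contributes to the estimate. Adjustment would lose no patients.

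**Working it through.** **Inputs.** Difference 30 points, SD 35 points, 36 per group, alpha 0.025, two-sample t-test, stated power 90% (Protocol 10.2.5 and SAP 4). Week 12 scans in 78 active and 38 placebo patients (Protocol, Amendment 6 summary). Two-sided testing is assumed, since sidedness is not stated. The within-arm correlation between baseline fat fraction and percent change, rho (absolute value), is **not given**; 0 to 0.5 is assumed.

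**1. The plan's own power.** SE = 35 × √(1/36 + 1/36) = 8.25, and 30/8.25 = 3.64. The noncentral t distribution gives 90.8%, against the stated 90%. For absolute change (difference 5.5, SD 6) it gives 94.3%, against the stated 94%. Both figures reproduce without a covariate, so the sample size matches the treatment-only model.

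**2. Precision, pooled active against placebo as in SAP 3.7.2.1.** Unadjusted SE = 35 × √(1/78 + 1/38) = 35 × 0.198 = 6.92. Adjusted SE ≈ 6.92 × √(1 − rho²), with one fewer residual degree of freedom.

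**3. Chance imbalance.** A 1-SE baseline difference between arms is √(1/78 + 1/38) = 0.198 baseline SDs. The unadjusted estimate then moves by rho × 35 × 0.198 points. For a 1.96-SE difference (0.388 SDs), replace 0.198 with 0.388. The baseline SD cancels, so none has to be assumed.

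| rho | SE | SE reduction | 95% CI half-width | Shift, 1-SE imbalance | Shift, 1.96-SE imbalance |
|---|---|---|---|---|---|
| 0 | 6.92 | 0% | 13.7 | 0 | 0 |
| 0.1 | 6.89 | 0.5% | 13.7 | 0.7 | 1.4 |
| 0.2 | 6.78 | 2.0% | 13.4 | 1.4 | 2.7 |
| 0.3 | 6.61 | 4.6% | 13.1 | 2.1 | 4.1 |
| 0.5 | 6.00 | 13.4% | 11.9 | 3.5 | 6.8 |

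The SE and half-width columns are for the adjusted model; the row for rho = 0 equals the unadjusted result. The shifts are in percentage points.

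**4. Power.** At 36 per group and alpha 0.025, adjustment would raise power from 90.8% to 93.3% (rho 0.3) or 97.0% (rho 0.5). For 78 against 38, unadjusted power at the planned effect is already 98.0% at alpha 0.025 and 99.0% at 0.05.

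**5. Validity of the unadjusted test.** In simulation with 78 and 38 patients and two-sided 0.05, at rho 0, 0.3 and 0.5, the treatment-only test rejected in 4.7 to 4.9% of null trials. With a true effect of −30, its mean estimate was −30.0.

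**The case against.** The strongest reply is that the omission is a rule rather than a slip. SAP 3.7.4.2 states it outright for lipids and 3.7.4.1 follows it for enzymes; percent change is already scaled by baseline. If true percent response is unrelated to baseline and scan noise is small, rho is near zero and adjustment gains nothing. The treatment-only test is valid, and the sample size was computed for exactly that test. Baseline-adjusted absolute-change and responder analyses are planned, as are subgroups at 20% baseline fat (SAP 3.7.2.4).

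Most of this stands. A reader might infer that the primary result is biased, that its p-value is too small or that the trial is underpowered; steps 1 and 5 show otherwise. A reader might also infer that precision is certainly lost; that depends on a correlation the documents do not give.

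The reply does not account for the wrong label, for adjusting the dichotomised endpoint but not the continuous one, or for the absence of any baseline-adjusted view of the primary variable.

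Timing is the other serious objection. The Amendment 6 summary reports the Week 12 primary readout, with group tables run in November 2017; SAP 1.0 was approved on May 15, 2018. Replacing the Week 12 primary model now would be a change made after its result was known. That objection stands and shapes the fix.

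**Conclusion.** The point holds in a conditional form. The primary model is mislabelled and leaves out a baseline covariate that is collected, complete in the evaluable population and used elsewhere for the same scans. If baseline fat predicts percent change, precision is given up and chance imbalance goes uncorrected.

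The size is modest: nothing at rho 0, about 5% of the SE at 0.3 and 13% at 0.5, with 1-SE shifts of at most 3.5 points against a planned effect of 30. These figures rest on the planned SD of 35, a linear relation with a common slope, and the assumed range of rho.

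This is a point about efficiency and transparency. It gives no ground for doubting the validity of the Week 12 comparison or for replacing it after the fact.

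**What to change.** 1. **Week 12 primary analysis.** In SAP 3.7.2.1, the Protocol Synopsis and Protocol 10.2.1.1, call the specified model a one-way ANOVA (two-sample t-test), keep it as the primary result, and state why baseline is left out.
2. **Sensitivity analysis.** Add `MODEL PCPDFF = Trt Base` to SAP 3.7.2.1 as a named sensitivity analysis reported beside the primary result, noting that it was added after the Week 12 group results were available.
3. **Percent-change analyses still unseen by treatment group.** Put baseline in the main model for Week 36 MRI-PDFF (SAP 3.7.2.5) and the later enzyme and lipid time points (3.7.4.1, 3.7.4.2). Record which results were unseen when the change was made. SAP 2.2.1 describes the extension in the past tense and says the treatment code was revealed during it, so this cannot be taken for granted. Where results have been seen, report the adjusted model as a sensitivity analysis instead.
4. **Consistency.** Amend the SAP 3.7.4.2 sentence that excludes baseline and its cross-reference to the primary model, give SAP 3.7.2.5 its own model statement, and align the Synopsis and Protocol 10.2.1.2, which applies the same ANCOVA to continuous secondary variables.

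The cost is a few lines of text in both documents, one extra table and one residual degree of freedom per adjusted model. No new data are needed.

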** PCPDFF = Percent change in MRI-PDFF from Baseline to Week 12  **
** Trt = Treatment group                                         **
*****
PROC GLM data=EFF;
  CLASS Trt;
  MODEL PCPDFF = Trt;
  LSMEANS Trt / e diff cl;
RUN;
```

In this analysis, the treatment group will be either MGL-3196 active or placebo. A pairwise comparison will be performed between MGL-3196 active and placebo. LS means for the treatment difference, 95% confidence interval and p-value will be provided.

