Rationale: Results of the 12 week MRI-PDFF primary endpoint readout of MGL-3196-05 have now been obtained in 116 patients treated with MGL-3196 or placebo who had both a baseline and Week 12 MRI-PDFF. The study remains blinded to individual patient treatment code. The primary endpoint was achieved. MGL-3196 treated patients versus placebo treated patients demonstrated [REDACTED] relative fat fraction reduction compared to [REDACTED] reduction in placebo [REDACTED] (see Table 1, supporting statistical data beginning on Page 8). A prespecified group of MGL-3196 treated patients [REDACTED] with higher MGL-3196 drug levels [REDACTED] demonstrated [REDACTED] fat reduction relative to placebo [REDACTED] of all MGL-3196 treated and [REDACTED] of the higher drug level group as compared with [REDACTED] of placebo patients attained $\geq 30\%$ liver fat reduction. Patients with lower drug exposure (MGL-3196, < 2700 ng*hr/ml) had less response [REDACTED] [REDACTED], significant relative to placebo [REDACTED]. The exposure groups were based on projected AUCs after dose adjustment, and an exposure of ≥ 2700 ng*hr/ml was chosen based on Phase 1 data that showed that there was a pharmacodynamic effect to lower lipids at this exposure.

There were statistically significant reductions in liver enzymes (ALT, AST) within the drug-treatment group that were also statistically significant relative to placebo in the group [REDACTED] of MGL-3196-treated patients with higher drug levels. Lipids, including LDL-cholesterol, triglycerides, apolipoprotein B and lipoprotein(a) were also significantly reduced in MGL-3196 treated compared to placebo patients. Triglyceride lowering appeared to be significantly attenuated at 12 weeks following the dose reduction at 4 weeks [REDACTED]

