### **3.6 Study Medication Exposure and Compliance**

Days of exposure to study medication will be summarized by treatment group for the Safety Population using descriptive statistics. Exposure in days is defined as the date of last dose of study drug minus the date of first dose of study drug plus 1. In addition, a contingency table will be provided to display the number and percentage of patients with exposure in the following categories:

- 1 to  $\leq$ 2 weeks (1-14 days),
- $>2$  to  $\leq$ 4 weeks (15-28 days),
- $>4$  to  $\leq$ 8 weeks (29-56 days);
- $>8$  to  $\leq$ 12 weeks (57-84 days),
- $>12$  to  $\leq$ 36 weeks (84-252 days), and
- $>36$  weeks (253 days or more).

Compliance will be calculated based on the total actual number of capsules taken as compared to the total expected number of capsules taken (2 per day). Percent compliance with the study medication during the 12-week Treatment Period (from Week 4 through Week 12) and the whole 36-week Treatment Period (from Week 4 through Week 36) will be summarized by treatment group for the Safety Population using descriptive statistics. Additionally, the number and percentage of patients within each treatment group with overall compliance in the following categories: <80%, 80% to 120%, and >120%, will be provided.

All the patients randomized to the active study drug group will take MGL-3196 80 mg. Based on the PK assessment and SHBG at Week 2, the dose at Week 4 may stay at 80 mg, it may be increased to 100 mg, or it may even be reduced to 60 mg. At Week 8 visit, the dose may be reduced to 40 mg. Duration of each dose level will be summarized, and number/percentage of patients taking each dose at each visit will be tabulated.

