## **4. SAMPLE SIZE DETERMINATION**

Approximately 117 patients in total will be randomized to 80 mg (2/3) or placebo (1/3) treatments. After PK assessment, a significant fraction of patients' combined AUC (MGL-3196 plus MGL-3196-M1) may exceed 5500 ng\*hr/ml resulting in a dose reduction to 60 mg. In order to power the study appropriately for an efficacious dose (which may be  $\geq 80$ mg), randomization may continue until approximately 36 patients have continued at Week 4 on the 80 mg dose. It is estimated that the treatment difference of percent change in hepatic fat fraction from baseline to Week 12 between any dose of MGL-3196 and the placebo group is about -30%. With a common standard deviation for the percent change in hepatic fat fraction at 35%, 36 patients per group completing the Week 12 visit will provide 90% power with a 2-sample t-test. The significance level is set as 0.025 for the consideration of multiplicity in comparisons of 2 daily dosing regimens of MGL-3196 versus the placebo group. The enrollment size is designed to allow for 10% drop out before the Week 12 visit, and as such, patients who drop out of the study will not be replaced.

With the sample size of 39 patients per treatment, the power for selected secondary efficacy endpoints was calculated. The baseline hepatic fat fraction is expected to be approximately 15% to 17%, thus the change from baseline to Week 12 in hepatic fat fraction is approximately -5.5% when comparing to placebo. With common standard deviation of change in hepatic fat fraction as 6%, 36 completed patients will provide 94% power for the study when evaluating the treatment effect in change of hepatic fat fraction.

In addition, the sample size is expected to provide meaningful liver biopsy-related data.

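### Cheap improvement: the primary interval pools one variance at 2:1 allocation, so its 95% coverage holds only if the arm SDs are equal, and the documents neither show nor rule that out

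*SAP*

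**What the plan says.** SAP 3.7.2.1 analyses the Week 12 percent change with PROC GLM and treatment as the only term: "MODEL PCPDFF = Trt". The comparison has two levels, since "the treatment group will be either MGL-3196 active or placebo", and for the primary result "LS means for the treatment difference, 95% confidence interval and p-value will be provided".

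Allocation is 2:1: "Approximately 117 patients in total will be randomized to 80 mg (2/3) or placebo (1/3) treatments". The Week 12 output in the protocol's Amendment 6 summary (Table 3.2) has 78 drug and 38 placebo patients.

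The only statement about spread is in SAP section 4: "With a common standard deviation for the percent change in hepatic fat fraction at 35" percent. It is a planning assumption.

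The drug arm does not stay on one dose. SAP 3.6 says "the dose at Week 4 may stay at 80 mg, it may be increased to 100 mg, or it may even be reduced to 60" (doses in mg), with 40 mg possible at Week 8. The Amendment 6 rationale reports that "Patients with lower drug exposure (MGL-3196, < 2700 ng*hr/ml) had less response".

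The model is reused. For liver enzymes, SAP 3.7.4.1 says "The same ANCOVA model for the percent change and change in hepatic fat fraction will be used". Lipids (3.7.4.2), Reverse T3 (3.7.4.3), fibrosis markers (3.7.4.4) and Week 36 MRI-PDFF (3.7.2.5) follow the same pattern.

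Neither document plans a variance check, arm-specific variances or robust standard errors for the Week 12 primary endpoint. The residual check in protocol 10.2.1.2 is for normality and sits under the secondary endpoints. The Per Protocol repeat (SAP 3.7.2) changes the population, not the model. The optional MMRM is listed under Week 36.

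**The concern.** A pooled-variance interval tolerates unequal SDs well when the arms are of equal size. At 2:1 it does not. The pooled variance gives the larger arm about two thirds of the weight, whereas the true variance of the difference gives the smaller arm's variance about two thirds. The two agree only when the SDs are equal.

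An effective drug can change the spread of percent change as well as its mean, and the plan has no analysis that would show whether the interval depends on this. At stake is the accuracy of the 95% interval for the main result and for the endpoints that reuse the model. The existence of an effect on liver fat is not at stake.

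**Working it through.** **Inputs.** Evaluable patients: 78 drug and 38 placebo (Amendment 6 summary, Table 3.2). Planning SD 35, difference 30 points, 36 per group, alpha 0.025, power 90% (SAP section 4). Exposure groups: 34 low and 44 high (Amendment 6 summary, Table 3.2.1). The observed arm SDs are redacted, so the SD pairs below are assumptions around the planned 35.

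**The plan's own figure.** Noncentrality = 30 / (35 × √(2/36)) = 30 / 8.25 = 3.64. With 70 df and two-sided alpha 0.025 (sidedness is not stated; two-sided assumed), power is 90.8%, against 90% stated. The figure is sound, but it is for 36:36 and equal SDs.

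**Pooled against true standard error at 78:38.**

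- Pooled SE = √{[(77·s₁² + 37·s₂²)/114] × (1/78 + 1/38)}, with √(1/78 + 1/38) = 0.1978.
- True SE = √(s₁²/78 + s₂²/38).

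In the pooled variance the drug arm has weight 77/114 = 68%. In the true variance its weight is 38/116 = 33%. Worked case, drug SD 25 and placebo SD 35:

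- pooled variance = (77 × 625 + 37 × 1225)/114 = 819.7, so pooled SE = 28.63 × 0.1978 = 5.66
- true SE = √(8.01 + 32.24) = 6.34
- ratio = 0.893, so the interval is built on an SE 11% too small.

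Coverage of the nominal 95% interval was simulated with 200,000 normal-data trials per SD pair. Repeating the simulation moved the pooled figures by less than 0.2 points.

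| Drug SD / placebo SD (assumed) | Pooled SE | True SE | Ratio | Coverage, pooled |
|---|---|---|---|---|
| 35 / 35 | 6.92 | 6.92 | 1.00 | 95.0% |
| 30 / 35 | 6.27 | 6.62 | 0.948 | 93.7% |
| 25 / 35 | 5.66 | 6.34 | 0.893 | 92.0% |
| 35 / 30 | 6.62 | 6.28 | 1.055 | 96.2% |
| 35 / 25 | 6.35 | 5.67 | 1.120 | 97.1% |

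An unequal-variance (Welch) interval covers 94.9% to 95.1% in every row. With arms of 36:36 the pooled interval keeps 94.9% to 95.0% at the same SD pairs, so it is the 2:1 split that makes unequal SDs matter.

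**What dose and exposure mixing does.** Suppose the SD is 35 within each exposure group and the group means differ by d points (d is assumed). Drug-arm SD = √(35² + (34/78)(44/78)d²) = √(1225 + 0.246d²). This is 35.3 at d = 10 and 38.0 at d = 30, a rise of 1% to 9%. At 38.0 against 35 the pooled SE is about 3% too large. Mixing alone therefore makes the interval slightly too wide.

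**Power at the 30-point effect.** Two-sided 0.05, 78:38: about 99% or more for the pooled and Welch tests at every SD pair in the table.

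**The case against.** The strongest reply is that any pooled test with unequal allocation is open to this remark, and that nothing in the documents shows unequal SDs here. That stands. The SDs are redacted, which is not a fault in the plan, and the one SD stated is a common 35%.

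A reader might infer that the mixed-dose arm makes the primary interval too narrow. The documents do not support this: mixing raises the drug-arm SD and errs on the wide side. The narrow case needs another mechanism, such as spread proportional to the fat that remains. Under that assumption a 30-point fall gives a drug SD of 0.7 × 35 = 24.5 and coverage of about 92%. No section of either document says that spread behaves so, and adding the mixing above pulls the SD ratio back to 0.72–0.83 and coverage up to between 92.0% and 93.4%.

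A reader might also infer that the primary p-value has an inflated error rate. If the drug changes nothing in any patient, both arms have the same distribution, the SDs are equal and the test keeps its level.

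It is also fair to say that the other endpoints are labelled exploratory without multiplicity control (SAP 3.7.4), that enzymes have an MMRM check and triglycerides a log or rank fallback, and that arm SDs appear in the planned summaries, so a reader could compute a Welch interval. None of these is a variance remedy, but they limit the harm.

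Finally, the Week 12 tables were run in November 2017 and SAP 1.0 is dated 15 May 2018. Replacing the primary variance estimator then would be a change made after group results were known. This objection is right and shapes the fix.

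**Conclusion.** The point holds as a low-cost improvement. The primary interval has its stated 95% coverage only if treatment leaves the spread of percent change unaltered, and the plan does not check this.

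The size is modest: an SD difference of 35 against 30 moves coverage by 1.2 to 1.3 points, and 35 against 25 moves it by 2.1 to 3.0 points. The direction is unknown. These figures rest on assumed SDs, normal data and the 78:38 split. The documents do not establish that the reported interval is wrong, that it is too narrow, or that the positive Week 12 conclusion is in doubt.

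**What to change.** Report both arm SDs beside the primary estimate. Add an interval with arm-specific variances: PROC MIXED with REPEATED / GROUP=Trt and Satterthwaite or Kenward-Roger degrees of freedom, or HC3 standard errors. The point estimate in 3.7.2.1 does not change.

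- **Week 12 MRI-PDFF and any other result already read:** present it as a labelled sensitivity analysis beside the pooled interval, not as a replacement.
- **Analyses not yet run that reuse the model** (Week 36 MRI-PDFF, enzymes, lipids, fibrosis markers): name it as the method before those data are read. SAP 1.2 carries no date, so the sponsor should record which analyses fall in each group.

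Cost: one extra SAS step. If the SDs are equal, the critical value goes from 1.981 (114 df) to 1.993 (about 73 df), and 1.993/1.981 = 1.006, so the interval is about 0.6% wider (mean width 27.5 against 27.4 points). Power is essentially unchanged.
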